| Study Design: | Pragmatic Interventional study | | |
| Primary Study | To determine and compare time to remission with treatment | | |
| Objective: | · | | |
| Secondary Study | To assess the effects of susceptibility factors on | | |
| Objective(s): | | | |
| | 2. To determine and compare rates of recurrence of PCT | | |
| | after treatment with low-dose hydroxychloroquine or | | |
| | phlebotomy. | | |
| Study Population and | Inclusion Criteria: | | |
| Main Eligibility/ | Willing to give informed consent | | |
| Exclusion Criteria: | 2. Willing to return to clinic or work with a local physician | | |
| | to have necessary labs done and samples sent to study | | |
| | site | | |
| | 3. Age 18 or greater | | |
| | 4. Women of child-bearing potential must be willing to | | |
| | avoid pregnancy and use an accepted and effective | | |
| | contraceptive method during treatment. | | |
| | 5. Well-documented PCT: | | |
| | i. Clinical features – A history of blistering | | |
| | cutaneous photosensitivity and/or skin fragility. | | |
| | ii. Biochemical findings – a and b are required | | |
| | a. A substantial increase in urinary porphyrins | | |
| | [>450 nmol/24 hours or g of creatinine, or | | |
| | more than 1.5-fold increase (relative to ULN | | |
| | of 300 nmol/24 hours or g of creatinine or | | |
| | >300 ug/24 hours or g of creatinine or | | |
| | than 1.5-fold increase (relative to ULN of 200 | | |
| | · | | |
| | ug/24 hours or g of creatinine)] and/or | | |
| | plasma porphyrins [>2.7 ug/dL, or >3-fold | | |
| | increase (relative to ULN of 0.9 ug/dL), and a | | |

| | fluorescence peak at ~619 nm]; a porphyrin | | |
|-------------------------|--|--|--|
| | pattern in urine or plasma showing a | | |
| | predominance of uroporphyrin and | | |
| | heptacarboxylateporphyrin, and normal or | | |
| | only slightly elevated urine ALA and normal PBG. | | |
| | b. Normal or only slightly elevated erythrocyte | | |
| | porphyrins [<200 ug/dL, or less than 1.5-fold | | |
| | increase (relative to ULN of 80 ug/dL)], | | |
| | unless elevated erythrocyte protoporphyrin | | |
| | are due to a non-porphyric condition in the | | |
| | opinion of the investigator. | | |
| | iii | | |
| | Exclusion Criteria | | |
| | Evidence for another cause of blistering skin | | |
| | lesions, such as another type of cutaneous | | |
| | porphyria, or pseudoporphyria | | |
| | 2. Pregnancy | | |
| | 3. Prior treatment by phlebotomy, | | |

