This study was initiated as a randomized study to compare treatment for PCT with phlebotomy or low-dose hydroxychloroguine, with retention of non-randomized patients in a substudy to provide additional safety data. Prior to this study becoming a Porphyrias Consortium (PC) protocol, 48 participants with well documented PCT and also characterized for the presence or absence of multiple known susceptibility factors were enrolled at one site and treated by phlebotomy or low dose hydroxychloroquine. Unexpectedly, an interim analysis found that fewer than half of the participants were eligible for randomization, and adherence to treatment and study visits was more difficult for study subjects than had been expected. The interim analysis of 30 randomized and nonrandomized patients who were evaluable because their data documented time to remission showed that for both treatments, time to achieving the primary outcome of a normal plasma porphyrin concentration averaged 6-7 months. The original randomized design did not meet the needs of feasibility and analysis for an inclusive, pragmatic study of a rare disease. Also, because follow up was short, the interim analysis did not establish that the two treatments are comparable in all important clinical respects. This revised protocol continues to follow standard of care procedures for these PCT treatments and includes longer follow up and additional treatment outcomes. Strengths of the study are: (1) it aims to enroll all patients who would otherwise undergo treatment for PCT; (2) it assures that all participants are characterized for multiple PCT susceptibility factors, including ethanol use, smoking, hepatitis C, HIV infection, estrogen use, HFE mutations and autosomal dominant

inheritance of a partial deficiency of uroporphyrinogen decarboxylase (UROD) due to *UROD* mutations (as in familial PCT); (3) it provides specific eligibility criteria for assignment to either treatment; (4) it randomizes participants eligible for both treatments, to avoid bias; (5) it defines primary and secondary outcomes for remission and aims to continue treatment until all are achieved; and (6) it provides follow up to compare recurrence rates after achieving remission. Visits are scheduled to document primary and secondary treatment outcomes based on the subject's laboratory values at each visit.

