Figure 2. Enrollment, assignment to treatment with or without randomization of 48 study patients with PCT in the interim analysis, and inclusion of the 30 patients who achieved a normal plasma porphyrin concentration in the analysis comparing time to remission with phlebotomy and low-dose hydroxychloroquine.

porphyrin level may not be a sign of full remission. Therefore, continuing treatment with

hydroxychloroquine until these additional outcome measures become normal may be beneficial. There were no significant side effects with either treatment. Follow up was insufficient to compare recurrence rates with these treatments.

Based on these interim findings we concluded that (1) the study should continue with changes to better assess response and durability with these two standard treatments. (2) Time to achieving treatment endpoints in addition to normal plasma porphyrin levels should be assessed. (3) All available PCT patients who require treatment should be enrolled, if possible, and assigned treatment based on medical indications, preference, or randomization (for patients suitable for either treatment). (4) A noninferiority design is not appropriate, because most subjects are not randomized, and outcomes should be compared using descriptive methods. (5) Power analyses to assess effects of clinical features and susceptibility factors should emphasize those of greatest clinical interest. We consider that age and sex are the clinical features of greatest interest, and alcohol use, hepatitis C and UROD mutations are susceptibility factors of greatest interest. (6) Longer follow up is needed to assess durability of treatment, and whether this relates to susceptibility factors. (7) The single primary outcome was evaluable in ~2/3 of patients in the interim analysis. Inclusion of additional outcomes is likely to provide evaluable outcomes for a greater proportion of patients. (8) This study also will provide serial data and samples on a cohort of PCT participants in whom treatment responses and complete remission are rigorously documented, which will be valuable for future cross sectional and longitudinal research on the pathogenesis and natural history of this disease.

3. Specific aims

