The primary working hypothesis for this study is that time to remission with low-dose hydroxychloroquine is comparable to phlebotomy for treatment of PCT. Because of the very different features of the treatments, the study will be unblinded, but the major outcomes in terms of efficacy will be measurements that are objective. The study follows standard of care procedures for treating PCT, but assures that all participants have well-documented PCT, are characterized for multiple susceptibility factors, are assigned to treatment based on consistent criteria, and documents remission and recurrence of the disease, which are aspects often not accomplished in clinical practice.

The specific aims for testing the hypothesis are:

- Enroll up to 100 participants, including those enrolled to date, in a prospective, unblinded study comparing treatment by phlebotomy with treatment by low-dose hydroxychloroquine. Specified eligibility criteria will be used for treatment assignment and participants eligible for both treatments will be randomized, to avoid bias. Tolerability and safety of both treatments will be assessed by interviews and questionnaires.
- 2. Times to defined primary and secondary treatment outcomes will be compared and subjects will be followed for up to 5 years to assess durability of treatment.
- 3. Characterize all participants for the presence or absence of known susceptibility factors for PCT, including ethanol use, smoking, hepatitis C, HIV infection, estrogen use, HFE mutations and an inherited partial deficiency of UROD (as in familial, type 2 PCT), the latter as assessed by measuring erythrocyte UROD activity and DNA studies for UROD mutations. Some of these factors (e.g. heavy ethanol use, HFE mutations) will influence treatment assignment, and all will be used to determine if individual susceptibility traits influence treatment response and durability.

Use of hydroxychloroquine for treatment of PCT is an off label indication. The results of this study will contribute to future efforts to modify product labeling for hydroxychloroquine to include a specific dosing regimen for treatment of PCT.

4. Research design and methods

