4.D. Recruitment and availability. Participants with PCT will be obtained primarily by referral to the participating centers. Physicians in primary care and specialty clinics such as dermatology and gastroenterology are made aware through personal contacts and notices of this treatment study and asked to refer participants. Notices are also sent to primary physicians and specialists in the referral area for each center in order to attract additional participants. We anticipate enrolling ~60 additional participants over the second 5-year cycle of funding of the Porphyrias Consortium to bring the total enrollment to at least 100. Thus the total target enrollment period will be 10 years.

Feasibility of recruitment is based on data from UTMB, which has been studying PCT and capturing all patients seen at that institution for many years. On average, we expect to enroll 8-10 patients with new onset or recurrent PCT per year at UTMB. Over the second 5-year period of Porphyrias Consortium funding we can expect to enroll a total of 40-50 patients at UTMB. With contribution from the other 6 centers, we expect to achieve the recruitment objective of ~60 new patients.

4.E. Enrollment and treatment assignment. Subjects will be enrolled if they meet the inclusion and exclusion criteria shown in Table 1, which should allow inclusion of the great majority of individuals who present with PCT. PCT patients are often unsponsored, and may be unable to afford either of the standard treatments in this study or to attend scheduled study visits. To assure both study adherence and optimal management, treatment and study costs will be covered either by participants' insurance or other funding if the participant does not have insurance, at the discretion of the study site. Reimbursement for travel and time lost for study participation will be at the discretion of each study site. This will help to enable all who need therapy for PCT to be treated within the study.

A history and physical examination will be carried out, which will help document the diagnosis and identify susceptibility factors such as alcohol and estrogen use and smoking, which will then be assessed in more detail by alcohol and smoking questionnaires. The results of the history, physical examination and screening laboratory tests will be recorded on Case Report Forms (CRFs) prepared for this study.

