4.I. Follow Up Phase. Determining durability of treatment after achieving a complete biochemical remission of PCT is an important objective of this study. Therefore, subjects will be observed long term during the Follow Up Phase for clinical and biochemical recurrences of PCT. This phase will begin after treatment is completed and all treatment outcomes are achieved. These visits will occur, either on site or remotely, every 3-6 months for up to 5 years, or possibly longer, depending on the availability of funding for the study. Symptoms will be monitored, and porphyrin levels measured for early detection of recurrence. Determinations on these visits will include total plasma and urinary porphyrin concentrations, plasma porphyrin neutral pH fluorescence emission peak, urinary porphyrin HPLC, ferritin and liver function tests. These samples may be obtained at the study site or elsewhere as part of standard of care. This will provide information on both clinical and subclinical biochemical recurrence after remission with both types of treatment. If a subject has a recurrence of symptoms their treatment will be followed clinically and they will continue with this follow up visit schedule.

It is important to assess both symptoms and porphyrin levels during follow up. In our experience patient reports of recurrence of skin manifestations are not always reliable, and can be discounted if evaluation at the time finds that porphyrin levels remain normal and no objective skin changes consistent with PCT are present. Conversely, biochemical recurrence with small or large increases in porphyrins can occur in the absence of symptoms. It is suspected that subclinical PCT may be especially common in patients with *UROD* mutations, but this is not well documented.

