- **4.J. Study duration and end of study.** The duration of the study including the Follow Up Phase is at least five years. It is possible that the study will be extended further depending on results and the availability of funding. Subjects will enter the study needing treatment, and require up to 24 months of treatment and observation to document achieving the treatment outcomes, followed by at least 3 years of follow-up. Therefore, the most frequent study visits will occur during the Treatment Phase and generally the first ~12 months of the study, which includes active treatment and the treatment outcome windows to document biochemical remission. Based on the interim analysis (45) it is anticipated that the first outcome (a normal plasma porphyrin concentration) will be reached within 6-7 months, on average. Other treatment outcomes should be achieved within ~12 months, although this is uncertain at present, since such observations were not part of the interim analysis.
- **4.K. Treatment outcomes and schedule of events.** A schedule of events in tabular form and a study flow diagram are shown below. This study compares time to reaching certain efficacy outcomes with the two treatments and documents durability of treatment in terms of absence of increases in porphyrins and recurrence of symptoms.

The primary efficacy outcome is achieving a normal plasma porphyrin concentration (<0.9 mcg/mL). Secondary efficacy outcomes include achieving (1) absence of a fluorescence peak in diluted plasma at neutral pH; (2) a normal level of total urinary porphyrins; (3) a normal pattern of individual porphyrins in urine (defined as total highly carboxylated porphyrins less than coproporphyrin); (4) times to achieving intermediate improvements in these porphyrin

measures, which will be defined during data analysis; (5) absence of new skin lesions for at least 3 months; and (6) effects of susceptibility factors such as hepatitis C, inherited UROD deficiency, etc. on achieving these treatment outcomes.

Durability of treatment (i.e. absence of recurrence) is recorded as beginning with the time that treatment achieves the treatment outcomes, and extends to the time of repeat documentation of a normal plasma porphyrin concentration, assuming there have been no interim recurrences of skin manifestations.

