The following susceptibility factors for PCT will be summarized and tabulated, and examined for balance across treatment groups. Differences in response based on susceptibility factors will be examined by multivariate analysis. The following susceptibility factors will be emphasized in this analysis:

- 1. Alcohol use (presence or absence)
- 2. Smoking (presence or absence)
- 3. Estrogen use (presence or absence)
- 4. Hepatitis C (presence or absence)
- 5. HIV (presence or absence)
- 6. UROD mutations (presence or absence)
- 7. HFE mutations (presence or absence of C282Y and H63D, and specific genotype combinations)

The analysis regarding susceptibility factors will take into consideration that some (e.g. homozygotes for HFE mutations with high ferritin levels) are medical reasons for assignment to one treatment group and not the other. We recognize that because the number of participants in subgroups based on susceptibility factors or combinations of susceptibility factors will be

relatively small, and it may not be possible to detect or exclude statistically significant differences for all susceptibility factors. The data is expected to support continuing this study with larger numbers of participants, or to suggest whether other studies should be designed to clarify the effects of these factors on treatment response and durability.

Additional modeling will assess factors affecting the frequency of recurrence and seasonality effects using logistic regression modeling and log-rank testing, respectively.

Sample Size and Power. A sample size calculation was performed to assess power for a study assessing the effect of factors on time to remission. Extremely common or rare factors are detected with 80% power for 90 subjects (and some dropout) when the hazard ratios are 2.3 (alcohol consumption and UROD deficiency), 2.2 (smoking history), 3.2 (estrogen usage), 2.0 (hepatitis C), and 1.9 (HFE mutations). In summary, this approach for times to remission leads to a sample size of approximately 50 subjects per group. All analyses were conducted in nQuery Advisor Version 5.0 (Janet Elashoff (2002); nQuery Advisor Version 5.0 User's Guide. Los Angeles, CA).

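### Factors affecting recurrence are to be modelled by logistic regression with no horizon, offset or censoring rule, although time at risk varies by design

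*Combined protocol and SAP*

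**What the plan says.** Section 4.R states: "Additional modeling will assess factors affecting the frequency of recurrence and seasonality effects using logistic regression modeling and log-rank testing, respectively". The statistical considerations in the synopsis carry the same sentence. Its closing adverb pairs logistic regression with recurrence and the log-rank test with seasonality, so the log-rank test does not supply a time-to-recurrence analysis. No horizon, person-time offset or censoring rule for recurrence is given.

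Time at risk differs between participants by design:
- 4.D: "Thus the total target enrollment period will be 10 years".
- 4.J: treatment and outcome documentation of up to 24 months, "followed by at least 3 years of follow-up".
- 4.I: visits "every 3-6 months for up to 5 years, or possibly longer, depending on the availability of funding for the study". This phase starts only once treatment is finished and every treatment outcome has been reached.
- Section 3: "subjects will be followed for up to 5 years to assess durability of treatment".

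On the interim analysis, the Background says: "Follow up was insufficient to compare recurrence rates with these treatments". The abstract says the revised protocol "includes longer follow up and additional treatment outcomes".

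Recurrence matters to the plan. A secondary objective in the synopsis is "To determine and compare rates of recurrence of PCT" after each treatment. The secondary outcomes add the effect of susceptibility factors on recurrence, and the study hypothesis in 1.B includes durability.

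Section 4.R applies Cox models to outcome measures, with time to remission as the example. The sentence before mentions durability but names no method for it. Section 4.K defines durability as an interval from achievement of the outcomes to a repeat normal plasma porphyrin, provided that skin manifestations have not recurred in between.

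**The concern.** In a yes/no logistic model, a participant free of recurrence at 3 years counts the same as one free at 5 years, and an early recurrence counts the same as a late one. The odds ratio then has no stated period and cannot readily be compared with another study. If one group is watched for longer, it has more opportunity to recur, and the odds ratio mixes risk with time observed.

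Differential follow-up is possible here. The Background reports that visits were missed more with phlebotomy, and 4.P allows removal for noncompliance. A factor that delays remission delays the start of follow-up, which shortens it if funding fixes the closing date. Under 4.E, patients with hepatitis C are first evaluated for another study, so hepatitis C status may be related to enrolment date. The documents do not show that any of these produced a difference, or in which direction.

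The treatment contrast has a separate gap. If the Cox wording does not reach recurrence, its model can be chosen after the data are seen.

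**Working it through.** The plan gives no recurrence rate, event count or power for recurrence, so there is no figure to reproduce. What follows is an illustration.

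**Inputs.** From the documents: follow-up of 3 to 5 years (4.J, 4.I); hepatitis C prevalence 69% (4.E); n = 90 (sample-size paragraph of 4.R). Assumed: constant recurrence hazard λ = 0.05, 0.10 or 0.15 per year; uniform follow-up; two-sided 5% tests. Results are listed in that order of λ. Fewer than 90 may be at risk, because follow-up starts only after all outcomes are achieved.

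**Formulas.** Recurrence by time t: p = 1 - exp(-λt). Averaged over follow-up uniform from a to b: p = 1 - [exp(-λa) - exp(-λb)] / [λ(b - a)]. Odds ratio: OR = [p1/(1 - p1)] / [p0/(1 - p0)].

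**1. Undefined period.** True hazard ratio 2, λ = 0.10:
- 3 years: p0 = 0.2592, p1 = 0.4512, OR = 0.8221/0.3499 = 2.35.
- 5 years: p0 = 0.3935, p1 = 0.6321, OR = 1.7183/0.6487 = 2.65.

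Over the three hazards the OR is 2.16/2.35/2.57 at 3 years and 2.28/2.65/3.12 at 5 years.

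**2. Half-year mean difference, no true effect.** Follow-up uniform 3.5-5 v 3-4.5 years (means 4.25 and 3.75), λ = 0.10:
- Longer group: p = 1 - (0.70469 - 0.60653)/0.15 = 0.3456.
- Shorter group: p = 1 - (0.74082 - 0.63763)/0.15 = 0.3121.
- OR = (0.3456/0.6544)/(0.3121/0.6879) = 1.16.

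Over the three hazards: 1.15/1.16/1.18. With the same follow-up distribution in both groups the OR is 1.00.

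**3. Error rates and power.** Simulation of 20,000 trials, exponential times, logistic likelihood-ratio test v log-rank, factor in 69%, n = 90:

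| Setting | Logistic, % | Log-rank, % |
|---|---|---|
| No effect, same 3-5 years | 5.7/5.2/5.1 | not listed |
| No effect, half-year difference | 6.6/6.6/7.0 | 5.1/5.2/5.2 |
| HR 2, same 3-5 years | 33.0/50.1/58.7 | 27.5/47.4/59.6 |
| HR 2, higher-risk group half a year shorter | 23.9/36.8/43.3 | 27.5/47.4/59.7 |
| HR 2, higher-risk group half a year longer | about 44/65/74 | not listed |

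A repeat simulation of the logistic cells agreed to within about two percentage points. With n = 60, the half-year null case gave 6.2/6.3/6.7%.

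**4. Power lost when follow-up is alike.** Hazard ratio 2, n = 90, logistic v a person-time Poisson model, both likelihood-ratio tests:
- Factor in 50%: 37.9/54.4/65.1% v 37.9/58.1/70.2%.
- Factor in 69%: 33.0/50.1/58.7% v 32.9/51.5/63.0%.
- Factor in 20%: 27.6/39.5/48.1% v 27.6/41.5/51.3%.

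The largest loss is 70.2 - 65.1 = 5.1 points.

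**5. Outer bound.** Every member of one group at 5 years and of the other at 3, no true effect: OR 1.76/1.85/1.97; false positives 16.4/24.6/31.8% (factor in 69%, n = 90).

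**6. Events.** With uniform 3-5 year follow-up and no factor effect, 90 × 0.181/0.329/0.449 = 16/30/40 recurrences.

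**The case against.** The bias depends on a condition that the documents do not show. With like follow-up the test is valid, and in two of the three hazard-ratio-2 cells the logistic test has more power than the log-rank, partly because the two tests are constructed differently. In the moderate null case the excess is only about 1-2 points of false positives. The power effect can go either way. All of this stands, and it limits the point to a worthwhile correction.

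It can also be said that 4.R does not spell out the logistic model: one fitted at a fixed 3-year horizon, or on visit intervals, would still be logistic regression and would be sound. That is fair, and it is why the criticism is of a simple yes/no model. But the plan states neither option, and the sentence as written leads naturally to the simple one.

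The study is declared descriptive, and 4.R already warns that subgroups will be small. That lowers the stakes. It does not supply a period for the odds ratio.

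A reader might infer that 4.I and 4.K give conflicting time origins, because 4.I starts follow-up after treatment ends. They do not conflict: 4.I dates the visit phase, while 4.K gives durability one start, achievement of the outcomes, for both treatments.

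**Conclusion.** The point holds as a defect in a stated method for a secondary outcome and should be corrected before analysis. A simple logistic model would give an odds ratio with no defined period and leave event times unused. If follow-up is distributed alike across groups, the cost is interpretability and at most about 5 points of power. If it differs by factor or treatment, the odds ratio is biased in a direction that cannot be known now. With a half-year mean difference, the null odds ratio is 1.15-1.18 and false positives are about 6-7%. With a true hazard ratio of 2, power moves from about 33/50/59% down to about 24/37/43% or up to about 44/65/74%. These figures rest on the assumed hazards, uniform follow-up, a factor in 69% and n = 90.

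A reader might infer that the planned recurrence results will be biased, or take the 5 v 3 year figures as expected. The documents do not support this: they show variable follow-up, not follow-up that differs by group, and the 5 v 3 year case is an outer bound. Nor do they show that the treatment comparison of recurrence lacks a model. The Cox wording may cover it; the text is ambiguous.

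One narrower gap remains in 4.K. The interval ends at a repeat normal plasma value, so a raised plasma value cannot extend it. But 4.K does not say what happens with a recurrence seen only in urine, or a biochemical recurrence followed by a later normal plasma value. The paragraph on treatment of recurrences in 4.F counts porphyrin rises as recurrence with or without skin signs.

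**What to change.** 1. In 4.R and in the matching synopsis sentence, replace logistic regression for recurrence with Kaplan-Meier and Cox analysis of time to recurrence. Start at the durability origin already defined in 4.K and censor at the last porphyrin test. Use this for the susceptibility factors, and state that the same model is used for the treatment contrast. A person-time offset, or one fixed common horizon, is an acceptable alternative.
2. In 4.K, state that the interval ends at the first recurrence as described in 4.F, including a biochemical recurrence without skin signs, or at censoring.

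The cost is wording in three places. Porphyrins are already measured every 3-6 months in follow-up and Cox models are already planned, so no visits or tests are added. There are downsides. Cox brings a proportional hazards assumption. Some early participants may lack dates for the later outcomes, which 4.J says were not part of the interim analysis. With only about 16-40 recurrences expected in 90 participants under the assumed hazards, few factors can be examined together under either model.
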